11.3.2 Macroscopic urinalysis

Quantitative urinalysis parameters will be summarized in the same manner as hematology and blood chemistry parameters. Response categories are negative, 1+, 2+, and 3+ for the qualitative urinalysis parameters occult blood, leukocytes, glucose, protein, and ketones and negative and positive for nitrates. Outcome values for these parameters are mapped to the levels Negative, 1+, 2+, and 3+ as follows for purposes of summary tables and the determination of PCST:

Category	Definition
Negative	“Negative”, “NEGATIVE”, or other outcomes that clearly reflect a negative finding
1+	“1+”, “+”, “Trace”, “TRACE”, or other outcomes that clearly reflect trace amount
2+	“2+” or “++”
3+	“3+”, “+++”, or other outcomes that clearly reflect the data above 3+ (eg, “4+”, “5+” etc) or more than 4 plus signs (eg, “++++”, “+++++”etc)

For qualitative urinalysis parameters (occult blood, leukocytes, glucose, protein, ketones, and nitrates), the number and percentage of subjects with each response category will be summarized for Baseline, Study Entry, each scheduled visit during the Evaluation Period for

which urinalysis parameters were scheduled to be assessed, Last Value, EDV, and FV. Percentages for each parameter will be relative to the number of subjects with a result at each time point.

For occult blood, leukocytes, glucose, protein, ketones, and nitrates, the number and percentage of subjects with an on-treatment PCST value, PCST low value, and PCST high value will be summarized. This summary will consider all assessments after the first dose of BRV and prior to or on the date of the last dose of BRV.

Additionally, for occult blood, leukocytes, glucose, protein, ketones, and nitrates, the number and percentage of subjects with a PCST value, PCST low value, and PCST high value will be summarized for Baseline, Study Entry, each visit during the Evaluation Period for which laboratory parameters were scheduled to be assessed, EDV, Last Value, and FV. Percentages for each parameter and time point will be relative to the number of subjects with a value at that time point.

11.3.3 Microscopic urinalysis

In microscopic urinalysis, a small sample of urine is centrifuged to remove the liquid. The sediment is then examined under a microscope. In the urinalysis laboratory test group, other than urinalysis parameters such as Bilirubin, Blood, Glucose, Ketone, Nitrite, pH, Protein, Specific Gravity, Total protein, Hemoglobin, Beta-HCG, Occult Blood, and Leukocytes, a listing of microscopic analysis parameters will be provided; no summaries of microscopic analysis findings are planned.

11.4 Vital signs, physical findings, and other observations related to safety

For subjects entering the study from N01315, the vital signs, physical findings, and other observations related to safety assessments will be provided in subject data listings only. The baseline assessment from the previous studies of these subjects will not be presented.

11.4.1 Vital signs

Vital signs are assessed at all FEVs, MEVs, YEVs, EDVs, and at FV, and may also be assessed at Unscheduled Visits. Body weight is assessed at all FEVs, YEVs, EDVs, and at FV, and may also be assessed at Unscheduled Visits.

Observed values for SBP, DBP, pulse rate, and body weight will be summarized for Baseline, Study Entry, each visit during the Evaluation Period for which vital signs or body weight were assessed, EDV, Last Value, and FV. Changes from Baseline for SBP, DBP, pulse rate, and body weight will be summarized for all post-Baseline time points.

The number and percentage of subjects with an on-treatment PCST value, PCST low value, and PCST high value will be summarized for SBP, DBP, pulse rate, and body weight. This summary will consider all assessments after the first dose of BRV and prior to or on the date of the last dose of BRV.

Additionally, the number and percentage of subjects with a PCST value, PCST low value, and PCST high value will be summarized for the above parameters for Study Entry, each visit

during the Evaluation Period for which vital signs or body weight were scheduled to be assessed, Last Value, EDV, and FV. Percentages will be relative to the number of subjects with a value at each time point.

PCST criteria (Section 13.3.4) are based on FDA Division of Neuropharmacologic Drug Products guidelines with some UCB-defined additions.

11.4.2 Electrocardiograms

ECGs are assessed at all YEVs, EDVs, and at FV, and may also be assessed at Unscheduled Visits.

The number and percentage of subjects with no abnormality, an abnormal but not clinically significant finding, and a clinically significant finding will be summarized overall. This summary will consider all assessments after the first dose of BRV and prior to or on the date of the last dose of BRV.

Additionally, the number and percentage of subjects with no abnormality, an abnormal but not clinically significant finding, and a clinically significant finding will be summarized for Baseline, Study Entry, each visit during the Evaluation Period for which an ECG is scheduled to be performed, Last Value, EDV, and FV. Percentages will be relative to the number of subjects with an ECG assessment at each time point. Subjects are counted at most once at each time point based on the worst observed outcome across all abnormalities reported at that time point.

A subject number listing will be provided that identifies subjects with a clinically significant finding after the first dose of BRV for each type of ECG abnormality.

11.4.3 Physical examination

A listing of abnormal physical examination findings will be provided; no summaries of physical examination findings are planned.

11.4.4 Neurological examination

A listing of neurological examination findings will be provided; no summaries of neurological examination findings are planned.

11.4.5 Psychiatric and mental status

A listing of abnormal Psychiatric and Mental Status findings will be provided; no summaries of Psychiatric and Mental Status findings are planned.

11.4.6 HADS

The scoring algorithm for HADS is described in 3.8.3.

During the first 2 years, HADS was assessed at Month 2, Month 6, Month 12, Month 18, and Month 24 and at EDV for subjects who discontinued the study prior to the YEV at the end of the second year for all subjects, and was also assessed at Month 4 and Month 9 for some subjects from N01114. HADS was not assessed for subjects from N01187 and N01236. Prior to integrated protocol amendment 25, HADS was being assessed for time points beyond the

YEV at the end of the second year. These additional assessments will not be summarized but will be provided in subject data listings.

[figure not shown]
Observed values for HADS depression and anxiety scores will be summarized for Baseline and Last Value for the Safety Analysis Set. Additionally, observed values will be summarized for Baseline and by visit for each study visit cohort. Summaries for each study visit cohort will only include scheduled visits up to the time of cutoff for the study visit cohort. Change from Baseline will be summarized at each visit during the Evaluation Period.

For summaries of observed values at each time point, only subjects with a change from Baseline value at that time point will be summarized. Additionally, the mean and SD for each Baseline score will be provided at each post-Baseline time point for subjects included in the summary of change from Baseline.

[figure not shown]
11.4.7 Columbia-Suicide Severity Rating Scale

With global amendment 25 to the protocol, the Columbia-Suicide Severity Rating Scale (C-SSRS) was added as an assessment at all study visits. Specific rules are provided to the study sites with regard to the identification of AEs or SAEs based on the outcome of this assessment. Because clinical events of interest will be recorded as AEs or SAEs, no study variable is defined for this assessment and no analyses are planned for the C-SSRS within the context of this study. However, subject data listings of the data for the C-SSRS will be provided. Additional listings will be provided for the subset of subjects with suicidal ideation and the subset of subject with actual suicide attempts.

Suicide ideation includes a “yes” answer to any 1 of the 5 suicidal ideation questions:

Suicide attempt includes response of a “yes” answer to any 1 of the 3 suicide attempt questions:

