- (k) QOLIE-31-P and HADS (not for ULD and N01315 subjects) are to be completed at the beginning of the visit by all subjects who are not mentally impaired.
- (l) The C-SSRS assessment will be implemented by site per IRB/IEC approval and upon completion of required training. As of the time of Protocol Amendment 26, all subjects had completed their EV. Thus, the C-SSRS was not assessed for any subjects at their EV.
- (m) The C-SSRS will be done at the AV in case the AV is conducted for safety and efficacy reasons.

Table 4:1 Study Flowchart

	Entry Visit (EV)	Full Evaluation Visit (FEV)	Minimal Evaluation Visit (MEV)	Yearly Evaluation Visit (YEV)	Additional Visit (AV)	Early Discontinuation Visit (EDV)	Down-Titration Phone Call (DTP) ^(p)	Drug-free Period Final Visit (FV)	Reference to Section
Assessments									

⁽ⁿ⁾ EQ-5D questionnaire is to be completed only by subjects coming from N01252 and N01254, and if not mentally impaired.

^(o) Socio-professional status is to be completed only by subjects coming from N01252 and N01254.

^(p) End of study status will be completed at the FV for subjects having performed an EDV (discontinued subjects) and for subjects leaving the study at the end of the program (completed subjects).

REDACTED COPY

This document cannot be used to support any marketing authorization application

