10.2.1 Informed Consent

Before any study-related procedures are performed, an IEC/IRB approved informed consent will be properly executed and documented.

For subjects already ongoing in the study, an IEC approved addendum will also be signed covering the increased risk of suicidality or suicidal thoughts to comply with the warning issued by FDA subsequent to an analysis performed on marketed antiepileptic drugs. Although data from brivaracetam studies were not included in FDA's analysis, this risk cannot be ruled out because brivaracetam belongs to this class of medications.

confidential information and ucb property

This document cannot be used to support any marketing, CEDEX COPY, or organization approval and any extensions or variations thereof.

Where legally acceptable, a Partner Pregnancy Consent Form will be issued in case the partner of a male subject becomes pregnant (Section 12.3.5).

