- Urinalysis: specific gravity, pH, glucose, bilirubin, ketones, occult blood, protein, nitrites, leukocytes. If the test for protein, blood or leukocytes shows a trace or is positive, sediment and microscopic analyses (erythrocyte cast, leukocyte casts, haemoglobin casts, uric acid crystals, bihydrate calcium oxalate crystals, monohydrate calcium oxalate crystals, triple phosphate crystals and bacteria) will be conducted.
- Where applicable (women with childbearing potential), a local urine pregnancy test (human chorionic gonadotropin [β -hCG] levels) will be conducted. In case of a positive outcome, a serum pregnancy test will be performed by the central laboratory. If pregnancy is suspected at any time during the study, an interim test should be performed.

Plasma samples to analyze brivaracetam and concomitant AED/AMD plasma concentrations have been collected up to Protocol Amendment 25, dated 03 Jan 2011, but will no longer be obtained.

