10.2.17 Adverse Events

At Entry Visit, the Investigator will record all the adverse events that were still ongoing at the end of the previous study. From Entry Visit onwards, adverse events will be assessed at each visit and recorded in the CRF and in the source documents. The study participant will be given the opportunity to report AEs spontaneously. A general prompt will also be given to detect adverse events, e.g., “Did you notice anything unusual about your health (since your last visit)?” In addition, the Investigator should review any self-assessment procedures (e.g. daily record cards) used in the study.

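### The C-SSRS arrived mid-study and changed how suicidality adverse events are found, yet the SAP tabulates no C-SSRS result and pools these events across the change

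*SAP*

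**What the plan says.** **Introduction of the scale.** SAP 11.4.7 records: "With global amendment 25 to the protocol, the Columbia-Suicide Severity Rating Scale (C-SSRS) was added as an assessment at all study visits". Protocol 10.2.16 dates that amendment when it says that plasma samples "have been collected up to Protocol Amendment 25, dated 03 Jan 2011". The footnotes to the flowchart in Protocol 4.1 add: "The C-SSRS assessment will be implemented by site per IRB/IEC approval and upon completion of required training". They also note that all subjects had passed entry by amendment 26: "Thus, the C-SSRS was not assessed for any subjects at their EV".

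**Link to AE reporting.** SAP 11.4.7 says that sites hold specific rules for identifying AEs or SAEs from the C-SSRS outcome. It then gives its reason for planning no analysis, "Because clinical events of interest will be recorded as AEs or SAEs", and concludes that "no study variable is defined for this assessment and no analyses are planned for the C-SSRS within the context of this study". Subject listings are planned, including listings of subjects with ideation and of subjects with attempts.

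**AE detection apart from the scale.** Protocol 10.2.17 provides for spontaneous reports and review of self-assessments such as the daily record card, and says: "A general prompt will also be given to detect adverse events". Protocol 10.2.10 adds a record of psychiatric and behavioral symptoms at the fuller visits.

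**AE tables.** SAP 11.2.2 plans TEAEs, and TEAEs of interest, by 3-month interval. SAP 3.2.5 counts the intervals from the first brivaracetam dose. The subgroups in SAP 4.8 are region, indication and previous randomized treatment.

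**The concern.** The SAP's reason for not analyzing the C-SSRS is that its events appear in the AE tables. But AE reporting is the channel whose sensitivity the C-SSRS may have changed. Some subject-time was observed without a structured suicidality questionnaire and some with one. The switch fell at different study months for different subjects, and always after entry. A 3-month table that combines both regimes mixes any change in risk with a change in ascertainment.

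The risk is one the protocol takes seriously. Protocol 10.2.1 requires a consent addendum on suicidality because "this risk cannot be ruled out because brivaracetam belongs to this class of medications". Long-term safety is the primary objective.

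No other planned summary fills the gap. HADS is summarized for the first 2 years only and was not assessed in ULD subjects (SAP 11.4.6). Psychiatric and mental status is listed, not summarized (SAP 11.4.5). No table shows how many subjects ever had a C-SSRS.

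**Working it through.** The plan contains no figure to reproduce: there is no sample size calculation and no testing. The check has two parts.

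**1. Does anything in the plan separate the two regimes?**

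- Time axis: days since first dose (SAP 3.2.5), not calendar or amendment time.
- Who is in an interval: every subject on brivaracetam at any time in it (SAP 11.2.2), at most 859 − 6 = 853 subjects once those from N01315 are excluded (SAP 2.4 and 3.5.1).
- Subgroups: none by C-SSRS status (SAP 4.8).
- AEs of interest: the search terms sit outside the SAP and suicidality is not named there. Suicidality terms still fall in the 3-month tables by system organ class and preferred term.

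So nothing separates them.

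**2. What can pooling do?** Let r be the true risk per interval, c the share of subject-time in the interval under the C-SSRS, s0 the detection probability without it and s1 with it. Then

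reported risk = r × [(1 − c) × s0 + c × s1].

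With r constant it cancels from the late-to-early ratio. All values of c, s0 and s1 below are assumptions; the documents give none.

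| s0, s1 | c from 0 to 0.5 | c from 0.1 to 0.9 | c from 0 to 1 |
|---|---|---|---|
| 0.8, 0.9 | 1.06 | 1.10 | 1.125 |
| 0.5, 0.8 | 1.30 | 1.45 | 1.60 |
| 0.3, 0.8 | 1.83 | 2.14 | 2.67 |

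Example, middle cell: early 0.9 × 0.5 + 0.1 × 0.8 = 0.53; late 0.1 × 0.5 + 0.9 × 0.8 = 0.77; ratio 0.77 / 0.53 = 1.45. If the two intervals have equal coverage (c = 0.5 in both), the ratio is 1.00 for every pair.

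Two features of the protocol work against this rise.

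- *Look-back.* Protocol 8.3.1 shows that the C-SSRS version for already enrolled subjects asks about the time since study start as well as before entry. AEs carry an onset date (Protocol 12.3.2.2), so an event recovered this way can fall in an early interval. If a fraction f of the missed early events is recovered, early detection becomes s0 + f × (s1 − s0). At f = 1 and full later coverage the ratio is 1.00. Subjects who left before roll-out contribute no recovery.
- *Withdrawal.* Protocol 8.3.1 ties withdrawal to certain C-SSRS answers, which removes higher-risk subjects from later time. If this (or anything else) halved later risk, the range 1.06 to 2.67 would become 0.53 to 1.33. A real halving can also be hidden: with detection going from 0.4 to 0.8, the ratio is (0.5 × 0.8) / (1 × 0.4) = 1.00.

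**The case against.** The strongest case for leaving the plan alone runs as follows. This is a single-arm study with descriptive summaries and freely adjusted dosing and concomitant drugs, so no time course isolates a drug effect. Suicidality AEs already have counts and denominators in the TEAE and SAE tables. Attempts leading to hospitalization or death met the general SAE definition whatever the C-SSRS found. The SAP also states its reason for the choice.

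Much of that stands. Constant ascertainment would still not give a causal estimate. But the change in ascertainment is an additional confounder that can be displayed, and the stated reason relies on the channel that changed.

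A reader might go further and infer any of three things the documents do not support:

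- *That earlier AEs were found only by the general prompt.* Spontaneous reports, diary review and the psychiatric status record were also in place, and POS and PGS subjects completed HADS in the first 2 years.
- *That early incidence is understated and a several-fold rise will appear.* No detection rates are given, roll-out was staggered, the first form looks back, and withdrawals act in the opposite direction.
- *That the listings will mix lifetime with on-study answers.* The ideation and attempt definitions in SAP 11.4.7 break off in the text available, and SAP 3.1 says that listings present source data, so this cannot be concluded.

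One further objection is sound and shapes the remedy: a single overall before/after split would stay confounded with time on drug, because C-SSRS follow-up always comes later than entry.

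**Conclusion.** The point holds as a limit on interpretation and a worthwhile, inexpensive improvement. It is not an error that invalidates the safety analysis. The introduction by amendment, the site-by-site start, the absence at entry, the rules feeding AE reporting, the lack of any C-SSRS table and the pooling by 3-month interval are all in the text. That detection improved is an inference from those rules and the less specific earlier methods.

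The size and net direction of the distortion cannot be derived from the documents. The ratios of 1.06 to 2.67 show what detection alone could do under the assumed values with constant true risk. They are not estimates, and the opposing forces could cancel or reverse them. What follows firmly is narrower: neither a rise, a fall nor a flat line in suicidality TEAEs over time on drug can be interpreted unless the two ascertainment regimes are separated.

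**What to change.** 1. **SAP 11.4.7.** Tabulate C-SSRS results by form version, with the number of subjects assessed and subject-years under C-SSRS follow-up. From the since-last-visit version, give n (%) with each ideation level and with attempts. Show answers from the version for already enrolled subjects separately, split into pre-study and since study start where the form allows.
2. **SAP 11.2.2.** Fix the suicidality search terms. Present these TEAEs by onset date before versus on or after each subject's first C-SSRS, within exposure-time intervals and not only as one overall split, with subject-years in each cell. Footnote the change in ascertainment, that earlier cells may include events recovered by look-back on the first form, and the C-SSRS-triggered withdrawals.

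The cost is SAP wording, one derived date per subject and two descriptive tables from data already collected and due to be listed. No new data, testing or change in conduct is needed. The drawback is few events and sparse cells, so any rate will be imprecise. Stratification separates ascertainment from time on drug but does not remove selection by withdrawal.

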13 APPENDICES

13.1 QOLIE-31-P total and subscale score calculations

The following outlines the calculation of the subscale scores for the QOLIE-31-P. The rescaled responses are provided for each item. The subscale scores are calculated by summing the rescaled responses for that subscale and dividing by the number of items with a non-missing response. Note that the divisors shown assume that all items for each subscale have a response; the divisor will differ if there are missing responses. A subscale score will be calculated only if at least 50% of the items within the subscale are present.

Scale/Item Numbers	Response						Subtotal	Final Score 0-100 point scale
	1	2	3	4	5	6		
Seizure Worry								
30.	0	20	40	60	80	100	_____	
31.	0	33.3	66.7	100	—	—	_____	
32.	0	50	100	—	—	—	_____	
33.	0	33.3	66.7	100	—	—	_____	
34.	100	75	50	25	0	—	_____	
							TOTAL : _____ ÷ 5 = _____	
Overall Quality of Life								
1.	Multiply each response by 10							
36.	100	75	50	25	0	—	_____	
							TOTAL : _____ ÷ 2 = _____	
Emotional Well-Being								
7.	0	20	40	60	80	100	_____	
8.	0	20	40	60	80	100	_____	
9.	100	80	60	40	20	0	_____	
10.	0	20	40	60	80	100	_____	
11.	100	80	60	40	20	0	_____	
							TOTAL : _____ ÷ 5 = _____	
Energy/Fatigue								
2.	100	80	60	40	20	0	_____	
3.	100	80	60	40	20	0	_____	
4.	0	20	40	60	80	100	_____	
5.	0	20	40	60	80	100	_____	
							TOTAL : _____ ÷ 4 = _____	
Cognitive Functioning								
19.	0	20	40	60	80	100	_____	
20.	0	33.3	66.7	100	—	—	_____	
21.	0	20	40	60	80	100	_____	
22.	0	20	40	60	80	100	_____	
23.	0	20	40	60	80	100	_____	
24.	100	75	50	25	0	—	_____	
							TOTAL : _____ ÷ 6 = _____	

Medication Effects

28.	0	33.3	66.7	100	—	—	_____
26.	100	75	50	25	0	—	_____
27.	100	75	50	25	0	—	_____

TOTAL : _____ ÷ 3 = _____

Daily Activities/Social Functioning

[figure not shown]
13.	0	20	40	60	80	100	_____
14.	0	25	50	75	100	—	_____
15.	0	25	50	75	100	—	_____
16.	100	75	50	25	0	—	_____
17.	100	75	50	25	0	—	_____

TOTAL : _____ ÷ 5 = _____

Total score is calculated as a weighted sum of the subscale scores based on the weighting shown below. Total score will be missing if at least 1 subscale score is missing. Total score will range from 0 to 100 with a higher score reflecting better functioning.

QOLIE-31-P Scale	Final Scale Score	Weight	Subtotal
Seizure worry (a)	_____	× 0.08	= _____
Overall quality of life (b)	_____	× 0.14	= _____
Emotional well-being (c)	_____	× 0.15	= _____
Energy/fatigue (d)	_____	× 0.12	= _____
Cognitive functioning (e)	_____	× 0.27	= _____
Medication effects (f)	_____	× 0.03	= _____
Daily activities/Social functioning (g)	_____	× 0.21	= _____
TOTAL SCORE: Sum subtotals (a) through (g)			_____

